# 10.8. Planned Interim Analysis

One interim analysis is planned at one month post Dose 3 of RTS,S/AS02D or Engerix-B, Clinic Visit 10. The interim analysis will be performed by the sponsor. In order to maintain blinding, the analyses will be performed by a statistician independent of the GSK Biologicals clinical teams. The interim analysis will be done on cleaned data and will contain analyses of reactogenicity, safety and immunogenicity.

This interim analysis will contain the final analyses for the reactogenicity (local and general solicited symptoms within 7 days of vaccination and unsolicited symptoms within 14 or 30 days of vaccination) and immunogenicity on Clinic Visit 1, 9 and 10.

# 10.8.1. Analysis of demographics/baseline characteristics

Demographic characteristics (age, gender) of each study cohort will be tabulated.

The mean age (plus range and standard deviation) by gender of the enrolled subjects, as a whole, and per group, will be calculated.

The distribution of subjects enrolled will be tabulated as a whole and per group.

# 10.8.2. Analyses of safety

Safety will be analyzed on the Total Cohort and the ATP cohort for Safety (for the purpose of reporting local reactogenicity the ATP will be used to ensure that those subjects who received vaccines in the wrong limb are not included).

The analysis of the occurrence of SAEs will be performed on the Total Vaccinated Cohort. The proportion of subjects with an SAE (until Clinic Visit 10), classified by the MedDRA preferred term level, reported from study start until study conclusion will be tabulated with exact 95% CI. Comparisons between groups will be done using Fisher's Exact test for each preferred term.

Serious adverse events and withdrawal due to adverse event(s), from study start until Clinic Visit 10 will be described in detail.

The percentage of subjects with at least one local adverse event (solicited and unsolicited), with at least one general adverse event (solicited and unsolicited) and with any adverse event during the solicited follow-up period will be tabulated with exact 95% CI after each vaccine dose and overall. The percentage of doses followed by at least one

local adverse event (solicited and unsolicited), by at least one general adverse event (solicited and unsolicited) and by any adverse event will be tabulated, overall vaccination course, with exact 95% CI.

The percentage of subjects reporting each individual solicited local and general adverse event during the solicited follow-up period will be tabulated with exact 95% CI. The percentage of doses followed by each individual solicited local and general adverse event will be tabulated, overall vaccination course, with exact 95% CI.

For all other solicited symptoms, the same tabulation will be performed for Grade 3 adverse events and for adverse events with relationship to vaccination.

For seizures occurring within 7 days of vaccination, an analysis will be performed based on the Brighton Collaborations guidelines [Bonhoeffer, 2004]. This includes descriptive tables of the time relationship of seizures to vaccination, the duration of seizures, the level of certainty and the relationship to episodes of fever.

The proportion of subjects with at least one report of unsolicited adverse event classified by the Medical Dictionary for Regulatory Activities (MedDRA), whenever available, and reported up to 30 days after vaccination (14 days after Dose 1, 2 and 3 of TETRActHib and after Dose 1 and 2 of RTS,S/AS02D or Engerix-B) will be tabulated with exact 95% CI. The same tabulation will be performed for Grade 3 unsolicited adverse events and for unsolicited adverse events with a relationship to vaccination.

Biochemistry (ALT, bilirubin, creatinine) and hematology (hemoglobin, WBC, platelets) values that are outside of the reference ranges will be described for timepoints Clinic Visit 1, 4 and 10.

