# Table 12Frequency of solicited symptoms per dose during the 4-day
follow-up period for each vaccine group (Total Cohort, Cohort 1,
Malaria-026)

R(1)<24; recipients of RTS,S/AS02A less than 24 months of age (Cohort 1)

C(1)<24; recipients of control vaccines (Prevnar & Hiberix) less than 24 months of age (Cohort 1)

R(1)>24; recipients of RTS,S/AS02A greater than or equal to 24 months of age (Cohort 1)

C(1)>24; recipients of control vaccines (Engerix-B) greater than or equal to 24 months of age (Cohort 1)

N = number of documented doses.

n/% = number/percentage of doses followed by a local/general symptom.

\*axillary body temperature  $\geq$  37.5°C.

Grade 3 injection site pain; cries when limb is moved/spontaneously painful.

Grade 3 swelling; > 20 mm.

Grade 3 fever; axillary body temperature  $\geq$  39.0°C.

Grade 3 drowsiness; drowsiness that prevents normal activity.

Grade 3 loss of appetite, not eating at all.

Grade 3 irritability/fussiness; crying that cannot be comforted/prevents normal activity.

Rel = related to study vaccine.

Note: all local injection site symptoms were considered related to study vaccine.

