# 2. OBJECTIVE(S)

# 2.1. Primary: Safety

• To describe the safety and reactogenicity of RTS,S/AS02D administered as 3 doses intramuscularly in the left thigh to infants at 10, 14 and 18 weeks of age, staggered with the administration of 3 doses of TETRActHib intramuscularly in the right thigh at 8, 12 and 16 weeks of age.

Refer to Section 10.1 for definition of the primary endpoint.

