#### 6.4.2. Randomization of subjects

Subjects will be allocated sequentially to treatment numbers in the order that they present for vaccination.

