#### **10.2.** Secondary endpoints

#### 10.2.1. Secondary endpoints for Safety

• Occurrence of unsolicited AEs after Dose 1, 2 and 3 of TETRActHib over a 14 day follow-up period (day of vaccination and 13 subsequent days)

- Occurrence of unsolicited AEs after Dose 1 and 2 of RTS,S/AS02D or Engerix-B over a 14 day follow-up period (day of vaccination and 13 subsequent days)
- Occurrence of unsolicited AEs after Dose 3 of RTS,S/AS02D or Engerix-B over a 30 day follow-up period (day of vaccination and 29 subsequent days)
- Occurrence of solicited general and local reactions over a 7 day follow-up period (day of vaccination and 6 subsequent days) after TETRActHib
- Occurrence of solicited general and local reactions over a 7 day follow-up period (day of vaccination and 6 subsequent days) after RTS,S/AS02D or Engerix-B.

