# 10.5.2. Sample size for secondary endpoint immunology of Hepatitis B response

This study will compare the immunogenicity of RTS,S/AS02D to Engerix-B. A noninferiority approach will be used to calculate the power of the study for the comparison of seroprotection rates and geometric mean titers of anti-HBs antibodies. The assessment of the anti-HBs antibody immune response will be based on approximately 200 evaluable subjects (100 subjects per group). This sample size will have 90% power at a 2.5% significance level using a one-sided equivalence test of proportions when the proportion that are seroprotected in the control group (subjects vaccinated with Engerix-B) is at least 0.97 and the proportion in the RTS,S/AS02D group is 0.97 and the maximum allowable difference between these proportions that still results in equivalence (the range of equivalence) is 0.10 (PASS 2000, one sided equivalence test of proportions, alpha = 2.5%).

Similarly this sample size will provide 98.5% power to demonstrate at a 5% significance level using an equivalence of means test, that the lower limit of a two sided 95% confidence interval on the GMT ratio of anti-HBs antibodies (RTS,S/AS02D vaccine

group over Engerix-B vaccine group ) is greater than 0.5 (2 fold decrease). (PASS 2000, equivalence of means, alpha = 5%). The standard deviation used for this calculation was 0.52 (computed on log base 10 transformed titers) and was derived from a GSK Biologicals study (Malaria-034) on 67 subjects which received three doses of RTS,S/AS02D administered at a 0, 1, 2 months schedule.

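### Section 10.8.2 puts exact 95% CIs on percentages of pooled doses as if a child's three doses were independent; with moderate within-child correlation these intervals are too narrow

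*Protocol*

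**What the plan says.** Section 10.8.2 of the protocol reports reactogenicity with two denominators. One is the child: "The percentage of subjects reporting each individual solicited local and general adverse event during the solicited follow-up period will be tabulated with exact 95% CI". Percentages of children with any local, any general or any event are also planned, after each dose and over the course. The other is the dose: "The percentage of doses followed by each individual solicited local and general adverse event will be tabulated, overall vaccination course, with exact 95% CI". The per-dose summary of any local, any general and any event is treated the same way ("solicited and unsolicited) and by any adverse event will be tabulated, overall vaccination course, with exact 95% CI"). Solicited Grade 3 and vaccine-related events follow the same tabulation.

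Randomisation is by child (section 6.4.2: "Subjects will be allocated sequentially to treatment numbers in the order that they present for vaccination"). The primary safety objective in section 2.1 has three doses of RTS,S/AS02D "staggered with the administration of 3 doses of TETRActHib intramuscularly in the right thigh at 8, 12 and 16 weeks of age", so each child gives three doses of the blinded vaccine and three of TETRActHib. Section 10.8 says the interim analysis holds the final reactogenicity results, so no later analysis in the protocol replaces these tables.

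**The concern.** An exact interval for a proportion has at least its stated coverage when the units counted are independent. Three doses given to one infant are repeated observations on the unit that was randomised. An infant prone to fever or injection-site swelling after one dose may well be prone to it after the next. Section 10.8.2 fixes both the unit (doses pooled over the course) and the interval (exact), with no allowance for this. Section 10.10.3.1 does allow for repetition within a child, through random effects for recurrent malaria episodes.

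What is at stake is the stated precision of a descriptive safety result. Reactogenicity is part of the primary objective and a secondary endpoint (section 10.2.1: "Occurrence of solicited general and local reactions over a 7 day follow-up period (day of vaccination and 6 subsequent days) after RTS,S/AS02D or Engerix-B"), in the first infants to receive this formulation. An interval that is too narrow overstates how well the per-dose rate is known.

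**Working it through.** **What the exact interval means here.** The protocol does not spell out the method, but the sponsor's earlier per-dose tables do so by example. Table 12 defines its denominator as "N = number of documented doses". For x events in n doses, the Clopper-Pearson limits are the 2.5% quantile of Beta(x, n−x+1) and the 97.5% quantile of Beta(x+1, n−x).

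| Source | x/n | Clopper-Pearson 95% limits | Printed limits |
|---|---|---|---|
| Table 12, pain, RTS,S/AS02A under 24 months | 165/558 | 25.8 to 33.5 | 25.8 to 33.5 |
| Table 12, fever, same group | 152/558 | 23.6 to 31.1 | 23.6 to 31.1 |
| Table 12, swelling, control under 24 months | 54/551 | 7.4 to 12.6 | 7.4 to 12.6 |
| Table 13, pain, RTS,S/AS02A under 24 months | 40/143 | 20.8 to 36.1 | 20.8 to 36.1 |
| Table 13, swelling, RTS,S/AS02A 24 months or older | 113/457 | 20.8 to 28.9 | 20.8 to 28.9 |

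Wilson limits do not match (for example 40/143 gives 21.3 to 35.8). The sponsor's per-dose intervals therefore count every dose as an independent trial.

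**Inputs for this trial.** There are 110 children enrolled and 100 evaluable per group (sections 3 and 10.5), with k = 3 doses of each vaccine per child. Per-dose rates of 5% to 30% are assumed. The upper end is in line with Table 12, where pain followed 29.6% and fever 27.2% of RTS,S/AS02A doses under 24 months. The within-child correlation ρ is not in the documents and is shown as a range.

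**Design effect.** Variance inflation = 1 + (k−1)ρ = 1 + 2ρ. This gives 1.1, 1.2, 1.4, 1.6 and 2.0 at ρ = 0.05, 0.1, 0.2, 0.3 and 0.5.

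**Coverage.** Each child's count was taken as beta-binomial with parameters p(1−ρ)/ρ and (1−p)(1−ρ)/ρ. The counts of 100 children were summed by exact convolution, and the probability that the exact interval on 300 doses contains p was read off.

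| Per-dose rate | ρ = 0 | 0.05 | 0.1 | 0.2 | 0.3 | 0.5 |
|---|---|---|---|---|---|---|
| 1% | 98.9% | 98.4% | 98.0% | 97.1% | 96.3% | 94.8% |
| 5% | 96.7% | 95.8% | 94.9% | 92.9% | 90.8% | 86.7% |
| 10% | 96.6% | 95.7% | 94.7% | 92.7% | 90.6% | 86.6% |
| 30% | 95.6% | 94.5% | 93.4% | 91.1% | 88.9% | 84.5% |

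Simulation with 110 children and rates of 5%, 10% and 28% agrees: 94.5% to 96.2% at ρ = 0.05, 91.1% to 93.4% at 0.2 and 84.3% to 86.7% at 0.5.

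**Width.** For 90 events in 300 doses (30%) the planned interval is 24.9% to 35.5%. On the effective sample size, 300/(1+2ρ):
- ρ = 0.2: 300/1.4 = 214.3, interval 23.9% to 36.6%, 19% wider
- ρ = 0.3: 300/1.6 = 187.5, interval 23.5% to 37.1%, 27% wider
- ρ = 0.5: 300/2.0 = 150, interval 22.8% to 38.0%, 43% wider

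**The case against.** The strongest reply is that little hangs on these intervals. The objective is to describe, and the endpoint is occurrence of reactions, with no per-dose metric named. Sound intervals per child, after each dose and overall, stand in the same section. The only between-group test in section 10.8.2 is Fisher's exact test on proportions of children with SAEs. The enrolment-suspension rule in section 5.1.6.2 applies a 5% threshold to a point percentage of doses, not to a confidence limit. All of this stands and bounds the consequence.

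It also stands that the size depends on a correlation the documents do not give. Clopper-Pearson is conservative, which absorbs a small correlation and protects events near 1% per dose. A rate that merely changes with dose number is not within-child correlation: with rates of 20%, 30% and 40% and no child effect, the variance ratio is (0.16 + 0.21 + 0.24)/3 divided by 0.21 = 0.97, slightly below 1.

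Two stronger readings are tempting and are not supported:
- A reader might infer that setting the two arms' intervals side by side would too often suggest a difference. With no true difference, 110 children per arm and the same beta-binomial model, the two planned intervals fail to overlap in about 0.4% of trials at ρ = 0 and at most 4.6% at ρ = 0.5. A dose-level test would have an inflated error rate, but the protocol plans none.
- A reader might infer that the per-dose rate is the chosen yardstick against earlier trials. No section says so. The earlier per-dose tables (2, 3, 6, 12 and 13) used a 4-day follow-up against 7 days here, and the one earlier RTS,S/AS02D table with 7 days (Table 14) is per subject.

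**Conclusion.** The point holds as a limited flaw in a descriptive analysis. The exact 95% CIs on pooled per-dose percentages ignore that each child contributes three doses, and they are too narrow when reactions are positively correlated within a child. For per-dose rates of 5% to 30% and 100 to 110 children per arm, coverage is about 95% to 96% at ρ = 0.05, 91% to 93% at 0.2, 89% to 91% at 0.3 and 84% to 87% at 0.5. The shortfall is material from about ρ = 0.2. It is negligible at about 0.05 or below, or for events near 1% per dose. These figures rest on an assumed correlation, a beta-binomial model, three doses per child, and reading the exact interval as Clopper-Pearson on doses, which the sponsor's own tables support. Point estimates are unaffected, as are the per-subject and single-dose intervals, the planned tests and the suspension rule.

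**What to change.** In section 10.8.2, for every percentage of doses pooled over the vaccination course, replace the exact 95% CI with a 95% CI that takes the child as the cluster. Any of these will serve: an exact interval on the effective sample size (doses divided by the estimated design effect), a GEE or robust-variance interval clustered on the child, or a bootstrap that resamples children. Name one. Keep exact intervals for per-subject and single-dose percentages. State that any between-arm remark on reactogenicity rests on the per-subject or the clustered per-dose figures.

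The cost is one sentence, a small programming change and somewhat wider intervals. No further data are needed.

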In this study all seizures occurring within a 30-day period of vaccination will be notified as SAEs. Complete data collection of seizures is sought to pilot an analysis proposed by the Brighton Collaboration [Bonhoeffer, 2004]. Key information pertaining to seizures will be documented in the CRF.

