# 10.9.1. Analyses of safety

#### 10.9.1.1. Primary endpoint

For the safety primary endpoint, the occurrence of SAEs will be performed on the Total Vaccinated Cohort. The proportion of subjects with an SAE, classified by the MedDRA preferred term level, reported from study start until study conclusion (end of the doubleblind phase) will be tabulated with exact 95% CI. Comparisons between groups will be done using Fisher's Exact test for each preferred term. If the percent of enrolled subjects excluded from the ATP cohort for analysis of safety is more than 5%, a second analysis based on this ATP cohort will be performed to complement the Total Analysis.

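### Seizures are collected for 30 days after vaccination in order to pilot the Brighton analysis, but the Brighton tables stop at 7 days

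*Protocol*

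**What the plan says.** Protocol Section 8.2 sets the collection rule: "In this study all seizures occurring within a 30-day period of vaccination will be notified as SAEs". It gives the purpose in the next sentence: "Complete data collection of seizures is sought to pilot an analysis proposed by the Brighton Collaboration". It adds: "Key information pertaining to seizures will be documented in the CRF".

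Section 10.8.2 specifies the analysis: "For seizures occurring within 7 days of vaccination, an analysis will be performed based on the Brighton Collaborations guidelines". Its content includes "descriptive tables of the time relationship of seizures to vaccination", together with seizure duration, level of certainty and relation to fever.

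The safety parts of the final and annex analyses (10.9.1 and 10.10.1) do not mention the Brighton tables, so 7 days is the only window the protocol gives them. No reason for it is stated.

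**The concern.** The same guideline is named as the reason for the 30-day collection and as the basis of the 7-day analysis. As written, the analysis uses only the first part of the period that was collected to feed it.

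What is at stake is the timing table. If it ends after day 6, it cannot set the first week against the later days, although the later seizures have been recorded. This is the first administration of RTS,S/AS02D to infants, and even one or two seizures would be worth describing in full.

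The protocol supplies an example. Section 1.3.3.2 reports that in Malaria-025 an RTS,S/AS02A recipient had a febrile convulsion 15 days after the second vaccination; it was judged unrelated. The same event here would be collected but left out of the Brighton tables.

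**Working it through.** The protocol states no day count for this point, so there is no figure to reproduce. The check counts calendar days inside and outside the windows.

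**Inputs**
- Vaccination days, Section 5.4: TETRActHib on Days 0, 30 and 60; RTS,S/AS02D or Engerix-B on Days 14, 44 and 74. All six count, because Section 8.2 refers to vaccination in general and the glossary lists TETRActHib as an investigational product.
- Day convention, borrowed from Section 10.2.1: "over a 7 day follow-up period (day of vaccination and 6 subsequent days" and "over a 30 day follow-up period (day of vaccination and 29 subsequent days". A 7-day window is therefore days 0 to 6 and a 30-day window days 0 to 29. The seizure sentences do not define their days.
- Dose intervals, Table 21: 12 to 21 days.

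**Nominal schedule**
- Union of 30-day windows: Day 0 to Day 74 + 29 = Day 103, with no gap, so 104 days.
- Union of 7-day windows: 6 × 7 = 42 days, with no overlap. 42/104 = 40%.
- Outside the 7-day windows: 104 − 42 = 62 days (60%).

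| Omitted days | Number | 30-day windows containing them |
|---|---|---|
| 7–13 | 7 | one (TETRActHib only) |
| 21–29 | 9 | two |
| 37–43 | 7 | two |
| 51–59 | 9 | two |
| 67–73 | 7 | two |
| 81–89 | 9 | two |
| 90–103 | 14 | one (RTS,S/AS02D or Engerix-B only) |
| Total | 62 | one: 7 + 14 = 21; two: 41 |

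Of the 21 omitted days with a single index dose, only the 14 from Day 90 to Day 103 follow the blinded vaccine alone. Days 7–13 come before its first dose.

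**The Malaria-025 example.** Fifteen days after a blinded dose is Day 14 + 15 = 29, 44 + 15 = 59 or 74 + 15 = 89. All three lie inside a 30-day window and outside every 7-day window; after the second dose the day is 59.

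**Sensitivity**

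| Assumption | Collected | In 7-day windows | Outside |
|---|---|---|---|
| Nominal | 104 | 42 | 62 (60%) |
| All intervals 12 days | 5 × 12 + 30 = 90 | 42 | 48 (53%) |
| All intervals 21 days | 5 × 21 + 30 = 135 | 42 | 93 (69%) |
| Days 0–7 and 0–30 inclusive | 105 | 6 × 8 = 48 | 57 (54%) |

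**Data cut.** On the nominal schedule the last 30-day window closes on Day 103, before Clinic Visit 10 on Day 104, which is the interim cut-off. At the 28-day minimum between Visits 8 and 10, only days 28 and 29 of that window fall on or after the visit.

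**The case against.** The strongest reply is that nothing here is contradictory. Section 8.2 is a reporting rule and does not promise a 30-day analysis window; collecting more widely than one table uses is ordinary practice. The 30-day capture has other uses: every SAE goes to the Local Safety Monitor and the DSMB as received (5.1.3.1, 5.1.4.1). Seven days is also a coherent choice. Temperature is recorded on days 1 to 6 (8.4.1), which suits the fever table, and 7-day windows never overlap, so each seizure has one index dose. What the Brighton guideline itself recommends cannot be checked from the protocol.

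Most of this stands. It shows that 7 days is defensible as a subset, but it does not answer the purpose given in 8.2. The temperature argument bears on the fever table only, not on timing, duration or certainty. The overlap argument can be met by showing time since each vaccine. Nor is this a detail left to an analysis plan, because the protocol itself fixes 7 days.

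A reader might infer three stronger things, none of which the protocol supports:

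- That later seizures go unanalysed. As SAEs they enter the preferred-term tabulation, with Fisher's exact test by term, "reported from study start until study conclusion (end of the doubleblind phase) will be tabulated with exact 95% CI"; the annex continues it to the end of the single-blind phase (10.10.1), and SAEs are also described in detail.
- That the tables can say nothing about timing. Days within the first week can be compared with each other, and there is a randomised Engerix-B arm. Only the comparison with days 7 to 29 is lost.
- That 60% of seizures would be missed. The count is of calendar days and gives no event rate.

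**Conclusion.** The mismatch between the stated purpose of collection and the specified analysis is real, and it is minor. It is confined to one set of descriptive tables; no endpoint, hypothesis test or stopping rule depends on them.

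The size, 62 of 104 collected days outside the 7-day windows, rests on the nominal dose days, on all six vaccinations counting, and on the day convention of Section 10.2.1. More than half of the collected days are outside under each alternative tried (53% to 69%). How many seizures this would leave out is unknown.

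**What to change.** In Section 10.8.2, run the Brighton tables on all seizures within 30 days of vaccination, by arm, with days 0 to 6 as a separate subset. For each seizure show two times: days since the last RTS,S/AS02D or Engerix-B dose, and days since the last TETRActHib dose.

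Add a table note with two caveats. Fever data are less systematic after day 6, when temperature is mainly recorded at a study visit or health-facility attendance. On the nominal schedule, 41 of the 62 added days have two candidate doses, because successive 30-day windows overlap from Day 14 to Day 89.

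The cost is one changed sentence and a somewhat larger descriptive table. The seizure information is already on the SAE form and CRF, and on the nominal schedule no later data cut is needed. The two caveats are the price of the wider window; keeping days 0 to 6 as a subset preserves what the present text would have delivered.
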